Transition zone biopsies will be performed at Visit 2, 30 days before treatment, and again at 3 months post-treatment. A total of 6 biopsy cores (i.e. 3 cores from the left and right transition zone) will be obtained from each volunteer. Prostate biopsy cores will be rapidly snap frozen in liquid nitrogen in coded and labeled containers and sent to [name] laboratory located at University of Texas Health Science Center - Houston Medical School for further processing.

A Randomization

Volunteers will be randomized using a blocked randomization approach by the MEDVAMC Research Pharmacy to either: ARM 1: onaBoNT-A 200 U prostate injection and placebo oral capsule daily or ARM 2: Placebo prostate injection (saline) and tamsulosin 0.4 mg capsule daily. Subjects will be randomized into one of the two treatment arms, using a block size of 4. The order in which the treatments are assigned in each block is randomized and this process is repeated for consecutive blocks of subjects until all subjects are randomized. This process ensures that after every fourth randomized subject, the number of subjects in each treatment group is equal. The MEDVAMC will prepare both pills (i.e. tamsulosin and placebo pill) and injections (i.e. onaBoNT-A and placebo saline injection) so that the study subject, investigator and all personnel treating or evaluating the subject will be blinded to treatment allocation.

B Schedule Of Events During Treatment Protocol

Tests/Time	Visit 1: Screening	Visit 2: Biopsy	Visit 3: Injection (4 weeks Post- biopsy ± 3 days)	Visit 4: Telephone Visit (Day 3 Post Prostate Injection)	Visit 5: Telephone Visit (1 Week Post- Injection ± 3 days)	Visit 6: (4 Weeks Post- Injection ± 3 days)	Visit 7: End of Study (3 months Post Injection ± 3 days)
Physical with DRE	X						X
Medical History	X						
Vital signs	X	X	X			X	X
Flowrate	X					X	X
PVR	X					X	X
PSA	X						X
CBC /platelet count	X						
Urinalysis (dipstick)	X	X	X			X	X
Biopsy(Transrectal Ultrasound Guided - TRUS)		X					X
Prostate Volume		X					X
Antibiotic		X	X				X
Fleets Enema		X	X				
Anesthesia (periprostate block)		X	X				
onabotulinumtoxin A or saline injection via TRUS			X				
Informed Consent	X						
Antibiotic dispensing	X	X				X	
Instructions to stop alpha blocker meds 7 days prior to biopsy	X						
Drug/Placebo dispensing			X			X	
Drug/Placebo accountability						X	X
AUA Symptom score	X					X	X
BPH Impact Scale	X					X	X
Bladder Function	X					X	X
Erectile Function	X					X	X

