The gene expression profiles in epithelial and stromal BPH cells of the prostates injected with onaBoNT-A and saline (i.e. Tamsulosin group), respectively, will be compared. Pre and post treatment biopsies will be frozen for laser capture microdissection and subsequent RNA extraction. All 6 biopsies will be frozen to guarantee adequate representation of both epithelia and stromal compartments of BPH. These sections will be used to orient laser capture microscopy in immediate frozen serial sections. Epithelial and stromal cells of the BPH nodules will be laser captured. Laser captured microdissection (LCM) tissues will be processed for gene expression profiling using Agilent Oligo Microarrays. Samples will be hybridized on a 4x44K slide formatted with the Whole Human Genome Oligo Microarray Kit that contains 41,000 unique genes and transcripts. Gene expression profiles will be evaluated using BioConductor software that will be used to process and normalize data. Significant differences in mean mRNA levels between groups will be determined with two-sided t-tests. Visualization of data (color maps) will be performed using Cluster and Java TreeView software. We will search for GO annotation terms in gene sets and will establish protein interaction networks analysis using the Human Protein Reference Database as we have reported previously and visualization will use Cytoscape software. Our next step is always to confirm the array analyses using qRT-PCR using pre-designed and validated primers when available. Otherwise primers will be designed and validated as described previously in numerous publications by [name] and our prostate research group. As a result of this study we will identify differential gene expression profiles in epithelial and stromal cells in the onaBoNT-A versus Tamsulosin treated prostates. In addition, we will be able to assess changes in gene expression profile before and after treatment with either agent. This analysis will permit us to assess whether Tamsulosin and onaBoNT-A have similar effects on human tissues as we have identified in rats. These results will serve as substantiation for further human clinical trials.

In addition to determining the effects of onaBoNT-A and tamsulosin on the genetic profile of human normal and BPH tissues, another goal is to determine the effects of

Tamsulosin and onaBoNT-A on the human BPH prostate tissue proliferation, apoptosis, innervation, stromal response, and angiogenesis.

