- C Urine specimens collected for dipstick analysis during the screening visit are routine for patients with BPH and LUTS and will be handled according to standard of practice. The test results will be included in the subject's research and medical charts.

X. STATISTICAL ANALYSIS

The primary endpoint, change in AUASS score from baseline to 3 months, between the onaBoNT-A and tamsulosin groups will be analyzed using the 2-sided independent t-test.

Baseline measures of the data such as age and ethnicity as well as secondary endpoints will be examined using summary statistics to determine if any differences exist between the 2 study groups.

Graphical methods will be used to access distributional properties of the secondary endpoints (urinary flow rate, serum PSA, prostate volume symptom relief, post-void residual, BPH impact score, Bladder Function, Erectile Function and Ejaculatory Function questionnaires). If extreme departures from normality are found, use of non-parametric analytical methods such as the Wilcoxon rank-sum test or transformation of the data will be considered. Questionnaire scores will be examined for reliability using Cronbach's alpha. The distributions of the scores will be examined to see if they are evenly distributed around the mid-point of the scales or are clustered at the top or bottom of the scales (ceiling or floor effect). If strong ceiling or floor effects are found, this could limit the usefulness of these measures. Changes in these secondary endpoints will be assessed using either the independent t-test or its non-parametric equivalent, the Wilcoxon rank sum-test. Statistical analysis will be done using SAS, version 9.2 (SAS Institute, Cary NC).

The endpoints apoptotic index, proliferation index, nerve density, stromal reactive indexes, and vessel density, will be checked for their distributional properties using the methods described for the data collected in Aim 1. Change from baseline to 3 months will be analyzed using either the 2 sided t-test or the Wilcoxon rank sum test.

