Statistical analysis of expression data will be performed similar to that of previous studies ⁴⁴, using public datasets of pathway-associated genes to identify general pathways involved. Our data indicates that epithelial cells are directly targeted by nerves. Denervation induces generalized atrophy of the epithelium and a significant decrease in protein production that cannot be reversed through supraphysiologic levels of testosterone. Mechanistically, denervation induces a translational and metabolic shutdown of the epithelial cells, which undergo a non-proliferative and more stem like phenotype with epithelial mesenchymal transformation. Particular emphasis will be given to specific markers within categories of genes we hypothesize onaBoNT-A treatment will have a greater impact given evidence within the BPH literature and our own experience with onaBoNT-A in rat and human prostate tissues: 1. Immune/Inflammation: IL-8, B cell homing chemokine, SRF:Serum response factor (c-fos serum response element-binding transcription factor), and MIC-1; 2. translation and translation initiation factor activity (signal transducer and activator of transcription 3, eukaryotic translation initiation factor 4A1, eukaryotic translation elongation factor 1 gamma*, eukaryotic translation initiation factor 3, subunit B, C and F); 3. Metabolic pathways (ST8 alpha-N-acetyl-neuraminide alpha-2,8-sialyltransferase);] 4. Growth Factors: IGF-2, FGF-2, IGF-I-R; and 5. Androgen Regulation: AR, ER β , RLS-HD, AKR1C1, AKR1C2, AR:ER β ratio, AKR1C1:AKR1C2 ratio. Corroborative studies will be performed with qPCR, immunofluorescence, and immunohistochemistry experiments.

XI. SAMPLE SIZE

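### The one between-arm gene-expression test named has no baseline term, although each man's pre-treatment RNA is collected, so the randomised comparison may lose precision

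*Combined protocol and SAP*

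**What the plan says.** Section VIII (Design) schedules tissue at two times: "Transition zone biopsies will be performed at Visit 2, 30 days before treatment, and again at 3 months post-treatment". Section IX.A sends both to the array work: "Pre and post treatment biopsies will be frozen for laser capture microdissection and subsequent RNA extraction".

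Section IX.A then sets up the contrast between the randomised arms: "The gene expression profiles in epithelial and stromal BPH cells of the prostates injected with onaBoNT-A and saline (i.e. Tamsulosin group), respectively, will be compared". The test named for it is: "Significant differences in mean mRNA levels between groups will be determined with two-sided t-tests". The sentence does not give the time point of the levels, and it mentions no baseline covariate, change score or arm-by-time term.

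The pre-treatment profile gets a role a few sentences later: "In addition, we will be able to assess changes in gene expression profile before and after treatment with either agent". No test is attached to that sentence, and it concerns change under each agent, not a comparison of the arms.

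Section X adds only a general reference: "Statistical analysis of expression data will be performed similar to that of previous studies". For the tissue indexes (apoptosis, proliferation, nerve density, stroma, vessels) the same section does use the baseline biopsy: "Change from baseline to 3 months will be analyzed using either the 2 sided t-test or the Wilcoxon rank sum test".

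**The concern.** Section IV.B makes the effect of the two drugs on RNA profiles part of the secondary objective. Men differ in their expression levels before any treatment. A t-test on levels leaves all of that stable between-man variation in the error term, and it makes no use of the baseline values to correct a chance imbalance between two arms of about 30 men. The data that could remove part of this variation come from a biopsy the men already undergo. The primary endpoint and the tissue indexes are both analysed as change from baseline, so expression is the one readout for which the stated arm comparison does not mention baseline.

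If r is moderate or high, a real difference in a marker that the investigators named in advance could be missed when the same samples would have shown it.

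**Working it through.** **1. The plan's own figure.** The only sample-size calculation is in Section XI and concerns the AUA symptom score: difference 5.6, SD 6.3, two-sided 0.05, 90% power, 29 per arm. The standardised difference is 5.6/6.3 = 0.889. By noncentral t, 28 per arm gives power 0.904 and 29 gives 0.914, so 29 is adequate. Allowing for 20% dropout, 29/0.80 = 36.25, rounded up to 37 per arm. The figure reproduces, but it says nothing about expression: no SD, effect size, correlation or power is stated for RNA.

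**2. Inputs for expression.**
- From the documents: two arms allocated 1:1 (Section VIII.A), 29 men per arm as the planned number with data (Section XI), 41,000 genes and transcripts on the array (Section IX.A).
- Assumed: pre/post correlation r of one transcript within a man, shown from 0.1 to 0.7; a true difference of 0.75 SD; 29 usable pairs per arm; nominal two-sided 0.05 for a single pre-named marker.

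**3. Formulas.** Relative to a t-test on post-treatment levels, the variance of the arm contrast is 1-r² with own baseline as covariate, and 2(1-r) with a change score. The noncentrality is d/√(f × 2/n), with d = 0.75, n = 29 and f the variance ratio. Degrees of freedom are 2n-2 = 56 for the t-test and the change score, and 2n-3 = 55 with the covariate.

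Levels only: 0.75/√(2/29) = 2.86, power 0.80.

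| r | Covariate: variance ratio | Equivalent men per arm (29/(1-r²)) | Power | Change score: variance ratio | Power |
|---|---|---|---|---|---|
| 0.1 | 0.99 | 29.3 | 0.81 | 1.80 | 0.55 |
| 0.3 | 0.91 | 31.9 | 0.84 | 1.40 | 0.66 |
| 0.5 | 0.75 | 38.7 | 0.90 | 1.00 | 0.80 |
| 0.7 | 0.51 | 56.9 | 0.98 | 0.60 | 0.95 |

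At r = 0 the covariate costs one degree of freedom and power stays at 0.80.

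**4. Limit of these powers.** They are for one marker at 0.05. As an illustration only, since Sections IX.A and X state no multiplicity rule for expression, take a Bonferroni level of 0.05/41,000 = 1.2 × 10⁻⁶. The same 0.75 SD difference then has power 0.011 on levels, 0.029 with the covariate at r = 0.5 and 0.10 at r = 0.7. Baseline adjustment helps the pre-named markers in Section X; it does not make the full screen well powered.

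**The case against.** The strongest reply is that the gain may be small. The two biopsies are different needle cores, microdissected separately and about four months apart, so r could be low for many transcripts. At r = 0.1 the benefit is less than one percentage point of power. The 0.75 SD effect is assumed too, and nothing guarantees 29 men per arm with usable paired RNA. All of this stands. It limits the size of the point but does not make the level comparison the better choice, because the covariate costs about one degree of freedom at worst.

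It can also be said that the plan is silent on baseline and does not exclude it: neither the groups nor the time point of the levels is defined, and Section X defers to earlier work. That is fair. The remedy is the same, because the model then needs to be stated.

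The different handling of the tissue indexes does not by itself show that expression is handled worse. A change score is less precise than levels below r = 0.5.

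Three stronger readings are tempting and are not supported:
- **Bias.** A reader might infer that ignoring baseline lets pre-existing differences pass as treatment effects. Allocation is randomised, so the test on levels is unbiased, and its type I error already allows for chance imbalance.
- **The only randomised molecular evidence.** The five tissue indexes come from the same biopsies and are also compared, and array results are to be confirmed by other assays.
- **A faulty slide layout.** The plan says "Samples will be hybridized on a 4x44K slide formatted with the Whole Human Genome Oligo Microarray Kit" and gives no allocation of samples to slides, so no poor layout can be read from it.

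**Conclusion.** The point holds as one of efficiency. The between-arm expression test, as written, makes no use of the pre-treatment profile, and no other section supplies a baseline-adjusted comparison of the arms. The pre-treatment biopsy is not wasted, since it serves the within-agent before/after assessment; the gap is confined to the randomised comparison.

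The size depends on an unknown r: a variance reduction of 1% at r = 0.1, 9% at 0.3, 25% at 0.5 and 49% at 0.7. It affects part of a secondary objective. The primary endpoint is untouched and no conclusion is biased. It is worth changing because the data are already being collected and the possible loss from adjusting is close to nil.

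**What to change.** Replace the t-test sentence in Section IX.A with:

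*For each transcript and compartment, post-treatment log2 expression will be compared between arms in a linear model with the same man's pre-treatment log2 expression as covariate (in BioConductor).*

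Use the covariate and not a simple change score, which loses precision when r is below 0.5. The wording also settles which time point and which groups are meant.

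The cost is one sentence of analysis plan. It needs no extra biopsies, arrays or visits, and the software is already named. The real downside is that men with only one usable biopsy do not fit the model directly, so the plan should say in advance how they will be handled.

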In summary, these studies suggest that nerves exert trophic effects on normal epithelial cells through the regulation of basic cellular processes such as gene expression, protein translation, and metabolism. The loss of nerve function induces a pattern of gene expression associated with survival and wound repair as well as a general atrophic phenotype in all experimental denervation conditions. These studies provide proof of principle that nerves have the ability to affect cell growth directly.

Our ability to measure meaningful changes in gene expression profiles in an orthotopic rat animal model and in a small group of human patients following chemical denervation with onaBoNT-A substantiate the need to apply these same methods to a greater extent in human prostate tissue following injection with onaBoNT-A. Such studies would allow for the identification of potential molecular targets highlighted by the onaBoNT-A effect for future investigation.

III. SIGNIFICANCE AND RATIONALE

Our proposed intervention is the first randomized clinical trial comparing the effects of onaBoNT-A prostate injection versus alpha adrenergic antagonist medication for LUTS

associated with BPH. Up to this point, clinical studies using onaBoNT-A in the prostate has been limited to patient's refractory to α -1 adrenoceptor blocker therapy. Our study will directly compare onaBoNT-A against α -1 adrenoceptor blockers as frontline therapy in a male veteran cohort suffering from moderate to severe LUTS. Besides its obvious efficacy in patients' refractory to α -1 adrenoceptor blocker therapy, onaBoNT-A injection has several potential advantages over oral agents. Focal prostate injection has been shown to be safe and obviates the systemic side effects observed with α -1 adrenoceptor blockers (i.e. orthostatic hypotension, sexual dysfunction). In addition, most clinical studies demonstrate a durable response to onaBoNT-A treatment exceeding 12 months. Although this study is of modest length (i.e. total 4 years), significant results could drive paradigm shifts in how LUTS associated with BPH is treated, even with regards to frontline therapy.

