Secondly, although sophisticated molecular techniques (i.e. LCM with Microarray Analysis) have been used by other investigators to characterize gene profile changes with BPH and LUTS, this will be the first study examining gene profile changes in BPH patients following treatment with the α -1 adrenoceptor blocker Tamsulosin or onaBoNT-A. This study is important because scant knowledge exists on the true mechanisms by which α -1 adrenoceptor blockers like Tamsulosin or onaBoNT-A improve patient urinary tract symptoms and quality of life. It is clear, however, that nerves not only regulate prostate growth and function but also account for LUTS that drive patients to seek therapy. This investigation will utilize onaBoNT-A as a biological tool to identify potential novel mechanistic pathways for future investigation that will push the development of targeted therapy to benefit those patients refractory to all pharmacologic treatment. Potential inflammatory pathways or neural sensory signaling alterations induced by BPH, which are modified by onaBoNT-A or Tamsulosin to improve symptoms via gene profile changes, can be explored by expert laboratories in the Texas Medical Center. This is a highly collaborative project utilizing expertise across departments that will foster translational work from the laboratory to the patient. Although not the primary goal of this study, we will also search for possible biological markers with prognostic value that could be confirmed in a future multi-center trial.

IV. OBJECTIVES

A Primary objective:

The primary objective of this Phase 2 clinical research study is to compare the efficacy of 200 U onaBoNT-A injected into the prostate versus oral tamsulosin for the treatment of lower urinary tract symptoms caused by BPH in male veteran volunteers at the Michael E. DeBakey Veterans Affairs Medical Center, Houston (MEDVAMC).

B Secondary objective:

The secondary objective is to determine the impact of tamsulosin and onaBoNT-A on the pathologic parameters and RNA profiles of epithelium and stroma in BPH tissues.

V. DRUG INFORMATION

A Botulinum toxin A is marketed in two pharmaceutical distinct formulations that are not equipotent in terms of mouse units. Differences in species sensitivities to different botulinum neurotoxin serotypes preclude extrapolation of animal-dose activity relationships to human dose estimates. For the purposes of this study, patients are

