 - b. Prostate size is measured via transrectal ultrasound on patients after receiving a Fleet's enema the morning of the examination. The patient is placed in the lateral decubitus position with knees tucked against the chest and the transrectal probe introduced. A multi-planar probe that gives a 112° sector image is used to allow viewing in both transverse and longitudinal planes without moving the probe. The prostate size is measured initially using the height (H), width (W), and length (L) functions available on the ultrasound machine. Scanning of the prostate is carried out in two planes at

right angles to each other. The height and width are identified on a transverse image and recorded. The length is identified and recorded in the perpendicular longitudinal plane. The volume is calculated as a machine function using the formula $H \times W \times L \times \pi/6$ and recorded on hard copy.

- OnabotulinumtoxinA or Saline placebo Injection
 - a. Anesthesia is delivered according to the clinical practice of the center PI. Transrectal periprostatic block may be used with a 5 ml bolus of 1% lidocaine given just superolateral to each seminal vesicle as visualized using the transrectal sound probe in the sagittal plane. The bolus is given via an appropriately long 22-gauge needle.
 - b. The onabotulinumtoxinA toxin type A solution is given via the same approach using a second needle.
 - i. For men randomized to the 200 unit onaBoNT-A arm, 50 units per 1.0 ml volume is given at the following points of the transitional zone: left and right inferior and superior transitional zone.
 - ii. For men randomized to the placebo arm, 1.0ml of saline is given at the following points of the transitional zone: left and right inferior and superior transitional zone.
 - c. The needle is passed from posterior to anterior through the peripheral zone (PZ) into the base of the prostate at the transition zone/central zone junction on the left side. The needle is advanced to superior aspect of the transition zone.
 - d. Prior to injection of onabotulinumtoxinA the needle is aspirated to insure that there is no blood return. This is repeated prior to each injection.
 - e. The initial 1.0 ml of solution is first deposited at the superior (bladder base) transition zone (TZ). The needle is withdrawn to the inferior (apex) transition zone/central zone junction and the second 1.0 ml of solution is deposited on the same side as the needle is withdrawn.

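### Within-arm before/after RNA changes cannot be attributed to either drug, because biopsy, needle injection and time are mixed in with them; label them descriptive

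*Combined protocol and SAP*

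**What the plan says.** The secondary objective (Section IV.B) is to "determine the impact of tamsulosin and onaBoNT-A on the pathologic parameters and RNA profiles of epithelium and stroma in BPH tissues".

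Section IX.A opens the RNA work with a comparison of the two randomised groups, and the only test it names is for that comparison: "Significant differences in mean mRNA levels between groups will be determined with two-sided t-tests". It then adds a second use of the data: "we will be able to assess changes in gene expression profile before and after treatment with either agent". The next sentence gives the interpretation: "This analysis will permit us to assess whether Tamsulosin and onaBoNT-A have similar effects on human tissues as we have identified in rats". No test, significance level or limit on interpretation is given for the before/after part.

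On sampling, Section VIII states: "Transition zone biopsies will be performed at Visit 2, 30 days before treatment, and again at 3 months post-treatment". It also states: "A total of 6 biopsy cores (i.e. 3 cores from the left and right transition zone) will be obtained from each volunteer". At Visit 3 (Section VIII.C) the onaBoNT-A arm is injected at four sites, where "50 units per 1.0 ml volume is given at the following points of the transitional zone". The other arm receives 1.0 ml of saline at the same four sites and takes active tamsulosin (Section VIII.A).

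For the tissue indices (apoptosis, proliferation, nerve density, stroma, vessels), Section X specifies a test on change from baseline to 3 months. It specifies no such analysis for RNA.

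**The concern.** The first tissue sample is taken before the transition zone has been injured by any study procedure. The second follows a multi-core biopsy and a four-site injection in that same zone. A change between them within one arm may come from the drug, the needles or the passage of time, and nothing in the design separates these within an arm.

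The overlap with the expected drug signature makes this more than a formality. The summary in Section II says of denervation: "The loss of nerve function induces a pattern of gene expression associated with survival and wound repair". Section X then gives priority to immune and inflammatory markers, including IL-8 and serum response factor. That tissue injury could move the same kinds of gene is an inference, which the documents neither show nor exclude. The sponsor's own earlier work had concurrent controls: control animals in the rat study and saline in the opposite lobe in the three-patient human study. The within-arm reading gives up that protection.

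At stake is a statement that one drug alters certain genes in human prostate as denervation did in rats, when biopsy and injection might have done so. Section IX.A intends these results to support further human trials, so a wrong attribution would carry forward.

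**Working it through.** **Where the sample size comes from.** No sample size is given for the RNA analysis, so the trial's own is used. Section XI assumes a difference of 5.6, SD 6.3, two-sided alpha 0.05 and 90% power. The exact two-sample t calculation gives 27.6, so 28 per group; the stated 29 gives 91.4% power. With 20% dropout, 29 / 0.8 = 36.25, so 37. The plan's figures hold, and the point does not depend on them. The checks below use 29 and 37 pairs per arm.

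**What each contrast estimates.** Write the expected post-minus-pre change for a transcript as:

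- onaBoNT-A arm: D_ona + P + T
- tamsulosin arm: D_tam + P + T

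D is the drug effect, P the effect of biopsy plus injection, and T the effect of time. P is taken as the same in both arms, since sites and volumes are the same.

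- Within-arm change estimates D + P + T. With no arm where D = 0, D cannot be isolated.
- The between-arm difference in change estimates D_ona − D_tam. P and T cancel.
- The between-arm difference in post-treatment levels also estimates D_ona − D_tam, because randomisation balances baseline in expectation.

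**How often a procedure effect would look like a drug effect.** Assumptions: D = 0; a shift d = P + T in units of the SD of the paired difference; a paired t-test, two-sided alpha 0.05 per transcript. Both d and the test are assumed, since the documents give neither.

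Rejection rate = 1 − F(t_c) + F(−t_c), where F is the noncentral t distribution with n − 1 degrees of freedom and noncentrality d√n. For n = 29, t_c = 2.048; for n = 37, t_c = 2.028.

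Example, d = 0.5, n = 29: noncentrality = 0.5 × √29 = 2.693, and the rejection rate is 0.739.

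| Shift d (SD) | Within-arm, n = 29 | Within-arm, n = 37 | Between-arm test of change |
|---|---|---|---|
| 0 | 5% | 5% | 5% |
| 0.2 | 18% | 22% | 5% |
| 0.3 | 35% (0.345) | 43% | 5% |
| 0.5 | 74% | 84% | 5% |
| 0.8 | 99% | >99% | 5% |

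A simulation (20,000 runs, n = 29; d = 0, 0.3, 0.5, 0.8) gave within-arm rates of 5.1%, 35.0%, 73.8% and 98.5%. The between-arm rate was 4.6% to 5.3% throughout.

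**Stricter alpha.** The array carries 41,000 transcripts, so 0.05 per transcript may not be what is used. At 0.001 with n = 29 the within-arm rates are 20% for d = 0.5 and 73% for d = 0.8. A stricter level lowers the rate but leaves the bias in place.

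**The case against.** The strongest reply is that the sound comparison is already the lead analysis. Section IX.A begins with the randomised groups, names a test only for them, and states its main result as a difference between onaBoNT-A and tamsulosin tissue. Before/after change is an addition with no decision rule. This stands. It confines the problem to the added analysis and the single-agent reading attached to it.

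Second, no procedure effect is documented. The follow-up sample comes about three months after injection and four after the first biopsy, and any injury response may have faded. This also stands: the shift could be zero, in which case the error rate is the nominal 5%. The wound-repair description came from controlled rat experiments and was accompanied by general atrophy, so it is not evidence of a needle artefact.

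Third, a reader might take the sentence on similar effects to mean that the two drugs will be declared alike if the same genes move in both arms. The documents do not support this. The sentence most naturally compares human tissue with rat tissue, and no rule ties significance in both arms to a claim that the drugs act alike.

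Fourth, a reader might infer that only a test on change removes the shared procedure effect, so that the planned test on mean levels is biased. It is not: under randomisation a comparison of post-treatment levels removes it too. Using each man's baseline is mainly a matter of precision.

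What remains unanswered is that no section limits how within-arm change is to be read, while Section IX.A reads it as each drug's effect.

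**Conclusion.** The point holds for the within-arm before/after RNA analysis only. That analysis cannot isolate either drug's own effect on tissue, and a procedure or time effect could be reported as one. Under the assumed paired test at 0.05 with 29 men and no drug effect, the chance of that for an affected transcript runs from 5% (no shift) through 18%, 35% and 74% to 99% (0.8 SD). The true place in that range is unknown.

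It would be wrong to conclude that the gene-expression study is invalid. The randomised comparison stands, on the assumption that biopsy and injection affect both arms alike. What it yields is onaBoNT-A relative to tamsulosin; an effect shared by both drugs, or that of tamsulosin alone, stays out of reach. The primary endpoint is untouched. Because this is a secondary, mechanistic aim, the severity is minor, and the change is a cheap improvement.

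**What to change.** Three wording changes in Sections IX.A and X:

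1. Make the randomised between-arm comparison the only inferential RNA analysis, and use each man's baseline sample in it. Either adjust the post-treatment level for baseline, or analyse change from baseline as Section X already does for the tissue indices.
2. Report within-arm before/after changes as descriptive, and state that they are confounded with biopsy, injection and time.
3. Qualify the sentence comparing human with rat effects: the trial estimates onaBoNT-A relative to tamsulosin and cannot isolate either drug's own tissue effect.

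The secondary objective need not be rewritten if this limit is stated.

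The cost is text only. Both biopsies are already planned for every man, so no arm, visit or sample is added. The downside is giving up single-agent claims about tissue effects, which the design cannot support.
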